## **Appendix 2. Diagnostic Criteria for Atopic Dermatitis**

Per Inclusion Criterion 3, a subject is to have a clinical diagnosis of atopic dermatitis according to the criteria of Hanifin and Rajka.

### **Hanifin and Rajka's Diagnostic Criteria for Atopic Dermatitis**

---

#### **Must have three or more basic features described below:**

Pruritus

Typical morphology and distribution:

Flexural lichenification in adults

Facial and extensor eruptions in infants and children

Chronic or chronically-relapsing dermatitis

Personal or family history of atopy (asthma, allergic rhinitis, atopic dermatitis)

---

#### **Must have three or more following minor features:**

Xerosis

Ichthyosis/palmar hyperlinearity, keratosis pilaris

Immediate (type 1) skin test reaction

Elevated serum IgE

Early age of onset

Tendency toward cutaneous infections (esp. staph. aureus and herpes simplex), impaired cell-mediated immunity

Tendency toward non-specific hand or foot dermatitis

Nipple eczema

Cheilitis

Recurrent conjunctivitis

Dennie-Morgan infraorbital fold

Keratoconus

Anterior subcapsular cataracts

Orbital darkening

Facial pallor, facial erythema

Pityriasis alba

Anterior neck folds

Itch when sweating

Intolerance to wool and lipid solvents

Periofollicular accentuation

Food intolerance

Course influenced by environmental and emotional factors

White dermographism, delayed blanch

---

### **Appendix 3. Prohibited Concomitant Medications**

Prohibited concomitant medication listed below should not be taken with study drug. Patients requiring treatment with a listed prohibited concomitant medication should be discussed with the Medical Monitor. Such subjects may still be eligible/continue in the study if they do not have to interrupt dosing with study drug for more than 28 consecutive days.

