**For China and Taiwan only:**

Subjects who are hepatitis B surface antigen (HBsAg) negative, hepatitis B core antibody (HBcAb) positive, and hepatitis B surface antibody (HBsAb) positive at Screening will have reflex testing for hepatitis B virus (HBV) DNA. Subjects who have HBV DNA above the lower limit of quantification (LLQ) will be excluded. Subjects who are HBV DNA negative or below LLQ may enroll but will have HBV DNA testing repeated at Weeks 12, 28, 40, 52, Rescue Week 12, and early termination from study during any treatment period.

- d. Have a history (single episode) of disseminated herpes zoster or disseminated herpes simplex, or a recurrent (more than one episode of) localized, dermatomal herpes zoster.
13. Have a history of alcohol or substance abuse within 6 months prior to Day 1 that in the opinion of the investigator will preclude participation in the study.
  14. A Screening 12-lead ECG that demonstrates clinically significant abnormalities requiring treatment (eg, acute myocardial infarction, serious tachy- or brady-arrhythmias) or that are indicative of serious underlying heart disease (eg, cardiomyopathy, major congenital heart disease, low voltage in all leads, Wolff-Parkinson-White syndrome) or criteria associated with Q wave interval (QT)/Fridericia-corrected Q wave (QTcF) abnormalities including:
    - A marked prolongation of QTcF interval (>450 milliseconds [ms]) on the screening ECG;
    - A history of additional risk factors for Torsade de Pointes (TdP) (eg, heart failure, hypokalemia, family history of Long QT Syndrome);
    - Use of concomitant medications that prolong the QT/QTcF interval.
  15. Have a known immunodeficiency disorder or a first-degree relative with a hereditary immunodeficiency.
  16. Have any malignancies or have a history of malignancies with the exception of adequately treated or excised non-metastatic basal cell or squamous cell cancer of the skin, or cervical carcinoma in situ.
  17. Require treatment with prohibited concomitant medication(s) ([Section 5.9.2](#) and [Appendix 3](#)) or have received a prohibited concomitant medication within the specified time frame prior to the first dose of study medication.
  18. Have evidence of active or latent or inadequately treated infection with *Mycobacterium tuberculosis* (TB) as evidenced by any of the following:

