## **5.9. Concomitant Treatment(s)**

Subjects must continue to avoid use of medications that have been washed-out prior to enrollment and will abstain from all concomitant medications as described in [Section 4.2](#) and [Appendix 3](#) of the protocol. Medications that are taken in the Screening/Washout period (after informed consent is obtained and before the first dose of investigational product on Day 1) will be documented as prior medications. Medications taken after the first dose of investigational product on Day 1 has been administered will be documented as concomitant medications. All concomitant medications taken during the study must be recorded in study records with indication (if Atopic Dermatitis), reference to any associated adverse event, dose, and start and stop dates of administration. Subjects will be queried about concomitant medication (including topical medications and treatments, over-the-counter and prescription medications and treatments, and vaccinations) at each study visit. Any new concomitant medications or dose changes to current concomitant medications should be evaluated for potential new or worsening adverse events.

Medicated topical therapies ie, a topical product that contains an active pharmaceutical ingredient indicated for the treatment of AD (irrespective of whether it is an over-the-counter [OTC] or prescription only product), are only permitted in this trial during the rescue period.

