### **5.9.2. Prohibited Medications and Treatments**

Subjects are required to discontinue and avoid using certain medications and treatments (see [Section 4.2, Inclusion Criteria](#) and [Exclusion Criteria](#), and [Appendix 3](#)). Subjects should be instructed at each visit to contact the study site investigator promptly if there are any intended changes or additions to concomitant medications.

All medications and treatments that could affect atopic dermatitis must be discontinued except oral antihistamines. Due to the potential to affect atopic dermatitis with ultraviolet light exposure, subjects must also avoid prolonged exposure to the sun and not to use tanning booths, sun lamps or other ultraviolet light sources during the study.

Subjects who received prior treatment with JAK inhibitors are to be excluded from the study.

Herbal medications with unknown properties or known beneficial effects for AD must be discontinued at least 4 weeks before the first dose of investigational product.

Restrictions on certain vaccinations are described in [Section 4.4.2](#).

The Pfizer study team is to be notified of any prohibited medications taken during the study. After consulting with the Medical Monitor, the investigator will make a judgement on the ongoing eligibility of any subject with prohibited medication use during the study.

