### **6.3. Double-Blind Maintenance Treatment Period**

#### **6.3.1. Visit 8, Day 85/Week 12 ( $\pm 3$ days) Randomization into Maintenance Treatment**

- Administer and score the Since Last Visit C-SSRS. For subjects meeting any of the criteria specified in [Section 7.5.1](#) a risk assessment by a qualified MHP should be done to determine whether it is safe for the subject to continue to participate in the trial;
- Administer PROs including: PtGA, DLQI (or CDLQI), POEM, HADS, EQ-5D-5L (or EQ-5D-Y in select countries), SF-36v2, Acute and FACIT-F (or Peds-FACIT-F). SF-36v2 will be completed by adult subjects only;
- Adolescents 12-17 years of age will not complete the SF-36v2. Adolescents 12-17 years of age will complete the CDLQI instead of the DLQI, the EQ-5D-Y in select countries instead of the EQ-5D-5L and Peds-FACIT-F instead of the FACIT-F;
- Review PSAAD daily completion (in selected countries) and pruritus NRS completion for this visit in the eDiary;
- Obtain weight for all subjects and height for adolescents only (12 to <18 years old);
- Obtain vital signs including pulse rate, blood pressure, respiratory rate and oral or tympanic temperature (after at least 5 minutes of rest);
- Perform a single 12-lead electrocardiogram (ECG);
- Conduct complete physical examination;
- Conduct clinical evaluations including IGA, SCORAD, EASI and BSA (calculated in the EASI);
- Obtain fasting samples for laboratory testing: serum chemistry, hematology (including coagulation panel, RBC/WBC Indices, lymphocyte subsets and markers), lipid profile, and urinalysis;
-  
- For China and Taiwan only: For subjects who had HBV DNA testing at Screening, collect blood sample for repeat HBV DNA testing;

- Urine pregnancy test (female subjects of childbearing potential including adolescents aged 12 years and older regardless of whether they have experienced menarche). A negative urine pregnancy test must be obtained prior to dosing with the investigational product;
- Determine if the subject meets all of the **responder criteria for randomization**:
  - a. IGA of clear (0) or almost clear (1);
  - b. A reduction in IGA from baseline (Day 1) of 2 points or more, and
  - c. Reaching an EASI-75 response compared to baseline;
- Review of Inclusion/Exclusion Criteria;
- Randomize subject if all responder and inclusion criteria are met, and none of the exclusion criteria are met;

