4.2. Per Protocol Analysis Set (PPAS)

The PPAS will be a subset of the FAS-RA consisting of subjects who had no major protocol violations. Subjects excluded from the PPAS will be determined and documented before the study is un-blinded. This set will include subjects who:

- Met key inclusion criteria (ie, IGA ≥ 3 , EASI ≥ 16 at Study Baseline, had documented prior qualifying treatment for AD).
- Met protocol-defined criteria for randomization (ie, responder for both IGA and EASI-75 at Week 12).
- Did not take a protocol-prohibited therapy for the primary diagnosis (ie, high potency or systemic medication or phototherapy) during the initial run-in period and during the randomized withdrawal period.
- Did not take a protocol prohibited (CYP2C19/CYP2C9 inhibitor and/or inducer drug) concomitant medication.
- Had an overall compliance of $\geq 80\%$ but $\leq 120\%$ with randomized study treatment.
- (if not flared), completed the study.
- Had no other major protocol violations that is likely to affect materially the clinical observations, or the outcomes of the subject determined by the clinical team.

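### The rules for subjects who need a prohibited CYP2C9/CYP2C19 drug conflict at entry and at Week 12, and the matching PPAS criterion has no time limit, so it reaches past flare

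*Protocol*

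**What the plan says.** **Eligibility and continuation.** Protocol Appendix 3 lists CYP2C9 and CYP2C19 inhibitors and inducers that are not to be combined with study drug. Patients who need one are to be discussed with the Medical Monitor, and then: "Such subjects may still be eligible/continue in the study if they do not have to interrupt dosing with study drug for more than 28" (days in a row).

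Exclusion 17 (Protocol Section 4.2) has two clauses. The first excludes a subject who requires a prohibited medication and points to Section 5.9.2 and Appendix 3. The second excludes those who "have received a prohibited concomitant medication within the specified time frame prior to the first dose of study medication". Neither clause states an exception. At Week 12, Section 6.3.1 instructs the site: "Randomize subject if all responder and inclusion criteria are met, and none of the exclusion criteria are met". Section 5.9.2 sets a further standard: after consulting the Medical Monitor, "the investigator will make a judgement on the ongoing eligibility of any subject with prohibited medication use during the study".

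**Per-protocol set.** SAP 4.2 keeps a subject in the PPAS only if, among other conditions, the subject "Did not take a protocol prohibited (CYP2C19/CYP2C9 inhibitor and/or inducer drug) concomitant medication". The bullet before it, on prohibited therapies for atopic dermatitis, is confined to use "during the initial run-in period and during the randomized withdrawal period". The CYP bullet has no such limit. Protocol Section 9.2.1 also counts prohibited concomitant medication as a major violation without naming a period. Protocol Section 5.9 separates prior from concomitant use at Day 1: "Medications taken after the first dose of investigational product on Day 1 has been administered will be documented as concomitant medications".

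**The concern.** A subject who requires a listed drug at entry or at Week 12 may be eligible under Appendix 3 and is barred under Exclusion 17 and Section 6.3.1. A site cannot tell from the text which passage governs, so similar subjects could be handled differently.

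The SAP issue is separate. If any use after Day 1 is concomitant and the CYP bullet has no end date, use in the 12-week rescue period counts. Only flared subjects enter rescue, so every subject removed for rescue-only use has an observed primary event. That makes membership of the PPAS depend on something that happens after the outcome. The SAP is also silent on a listed drug taken during a pause that Appendix 3 contemplates.

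**Working it through.** **1. Eligibility passages side by side**

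| Subject | Appendix 3 | Exclusion 17 and Section 6.3.1 | Section 5.9.2 |
|---|---|---|---|
| Requires a listed drug at entry | May be eligible, subject to the 28-day limit | Barred | Judgement clause addresses use during the study |
| Requires it at Week 12 | May continue, same limit | Barred from randomization | Case-by-case judgement, no 28-day limit |
| Course begun and finished in run-in | May continue, same limit | Not clearly caught: the need has passed, and clause 2 looks only before the first dose | Case-by-case judgement |
| Requires it after randomization | May continue, same limit | No further re-check scheduled | Case-by-case judgement |

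The direct conflict is in the first two rows. In the last two, the 28-day limit and the open judgement differ without opposing each other. The number of subjects affected cannot be derived from the documents.

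**2. Reach of the PPAS criterion**

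- In SAP 4.2 the atopic dermatitis therapy bullet has a period, the compliance bullet refers to randomized treatment, and the completion bullet is conditional on not having flared. The CYP bullet has none of these limits.
- Flare (SAP 3.1) requires an EASI loss and an IGA of 2 or higher. The key secondary event (SAP 3.2) is an IGA of 2 or higher. At flare both have therefore occurred, and a drug first taken later cannot alter either event time.

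**3. Size of the post-flare deletions**

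The documents give no rates. Assumptions: 200 per arm as planned; 75% flare on placebo and 20% on 200 mg; 5% to 20% of subjects starting a listed drug per year; the same rate in flared subjects of each arm. Crude event proportions serve as the gauge.

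- Use over 12 rescue weeks, 1 − (1 − p)^(12/52): p = 0.05 gives 1.2%; p = 0.20 gives 5.0%.
- Placebo: 150 flares, so 1.8 to 7.5 subjects removed.
- 200 mg: 40 flares, so 0.5 to 2.0 removed.
- At the upper end, placebo is 142.5/192.5 = 74.0% (from 75.0%) and 200 mg is 38/198 = 19.2% (from 20.0%). The difference is 54.8 points (from 55.0).

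A harsher case assumes 10% use in rescue and flare rates of 80% and 20%. Placebo is then 144/184 = 78.3% and active 36/196 = 18.4%, so the difference goes from 60.0 to 59.9. With 80% and 40%, active is 72/192 = 37.5% and the difference goes from 40.0 to 40.8. The shift can go either way and stays under 1 point.

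**4. Use during a pause**

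- Randomized treatment lasts 40 × 7 = 280 days. A 28-day pause is 28/280 = 10%, leaving 90% compliance if paused days count as missed.
- Compliance falls below 80% from the pause alone only when randomized treatment lasts under 28/0.20 = 140 days. For longer treatment the CYP bullet, not the compliance bullet, decides PPAS membership.
- The washout examples in Appendix 3 reproduce: carbamazepine, 5 × 15 h = 3.1 days, plus 14 = 17.1 (stated 17); fluoxetine through norfluoxetine, 5 × 16 = 80 days (stated about 80). Since 80 exceeds 28, a listed drug taken during a pause can still be present when study drug restarts.

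**The case against.** **The eligibility passages can be read together.** Exclusion 17 cites Appendix 3, so the specific provision may be meant to qualify the general criterion, and Medical Monitor discussion limits divergence between sites. This narrows the problem. It does not remove it: the citation may simply identify the prohibited drugs, no exception is stated, and discussion does not say which passage prevails. A reader might also infer that any listed drug taken in run-in bars randomization. The text does not support that, as the third row of the table shows.

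**Staying in the study and leaving the PPAS are compatible.** This is right. Protocol 9.2.1 makes prohibited medication a PPAS violation, and the SAP follows it. Nothing contradictory follows from a subject continuing under Appendix 3 and being left out of the PPAS.

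**Rescue use is caught only by silence.** No passage says that post-flare use counts. Section 5.9 is a recording convention, the SAP treats entry to rescue as dropout from randomized treatment, and the last PPAS bullet speaks of violations likely to affect outcomes. The team may well intend the narrower reading. Even so, the neighbouring bullets carry limits and this one does not. Deciding exclusions before unblinding fixes when the rule is applied, not what it covers.

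**The deletions are trivial.** A reader might infer that removing events mainly from placebo distorts the comparison. More placebo events are removed, but in the assumed scenarios the difference barely moves.

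**Conclusion.** The point stands in two limited parts. First, Appendix 3, Exclusion 17, Section 6.3.1 and Section 5.9.2 do not give one answer for a subject who requires a listed drug at entry or at Week 12. The documents do not show which rule is intended. Second, the CYP criterion in SAP 4.2 lacks a period, so its literal reading excludes flared subjects on information that arises after both time-to-event endpoints.

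The statistical effect is small. With up to 5% of flared subjects using a listed drug in rescue and flare rates of 75% and 20%, the event proportion falls by about 1 percentage point or less per arm, and the difference changes by about 0.2 points. All of these rates are assumed. The PPAS analyses in SAP 6.1.1.2 and 6.2.1.2 are supportive. FAS-RA, the primary analysis and the test hierarchy are unaffected, and no conclusion of the trial is shown to be at risk.

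It would be tempting to add that use during an Appendix 3 pause should not count as a violation because study drug is not being taken. The documents do not settle that, and the washout times in Appendix 3 give a reason for caution.

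**What to change.** 1. **Protocol.** Reconcile Appendix 3, Exclusion 17, Section 5.9.2 and Section 6.3.1 so that one stated rule covers entry, Week 12 and continuation. Which rule that is belongs to the sponsor.
2. **SAP 4.2.** Limit the CYP bullet to use in the run-in and randomized periods, up to flare or last randomized dose, in line with the bullet before it. Protocol 9.2.1 could carry the same limit.
3. **SAP 4.2.** Have the sponsor state whether use during an Appendix 3 pause counts as a PPAS violation, taking the Appendix 3 washout times into account.

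The cost is a sentence or so in each document. Medication start and stop dates and dosing records are already collected, so no new data are needed. Under item 2 the PPAS becomes slightly larger.

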#### **CYP2C19 Inhibitors**

Fluconazole (Diflucan)  
Fluvoxamine (Luvox)  
Ticlopidine (Ticlid)  
Esomeprazole (Nexium)  
Fluoxetine (Prozac)  
Moclobemide  
Omeprazole (Prilosec)  
Voriconazole (Vfend)

#### **CYP2C9 Inhibitors**

Fluconazole (Diflucan)  
Amiodarone (Cordarone)  
Fluvoxamine (Luvox)  
Miconazole  
Oxandrolone (Oxandrin)  
Voriconazole (Vfend)

#### **CYP2C19 Inducers**

Enzalutamide (Xtandi)  
Rifampin

#### **CYP2C9 Inducers**

Carbamazepine (Tegretol)  
Enzalutamide (Xtandi)  
Rifampin

The washout period for all Cytochrome P (CYP) 2C9 and CYP2C19 inhibitors is 1 week or 5 half-lives, whichever is longer.

The washout period for all CYP2C9 and all CYP2C19 inducers is 5 half-lives plus 14 days prior to the first dose of investigational product. For example, the average half-life of Carbamazepine after repeat dosing is in average 15 hours. The washout period is calculated as the sum of 5 half-lives (approximately 3 days) and an additional 14 days for a total of 17 days.

This is not an all-inclusive list. Study personnel should stay current and consult with their pharmacy to exclude all concomitant medications that are CYP2C9 or CYP2C19 inhibitors or inducers. Half-life refers to half-life of the parent drug and its metabolites which are inhibitors or inducers. The longest half-life should be used to calculate the period necessary to washout a medication prior to the first dose of investigational product. For example, fluoxetine and its metabolite norfluoxetine are both inhibitors of CYP2C19. The terminal half-life of fluoxetine is up to 6 days; however, norfluoxetine has a longer half-life, up to 16 days. Therefore, the washout period should be calculated based on 5 times the half-life of norfluoxetine, for a total of approximately 80 days prior to the first dose of investigational product.

Use of concomitant medications that prolong the QT/QTcF interval were exclusionary for enrollment in the study. After the completion of enrollment the restriction on these prohibited medications was removed.

## **Appendix 4. Guidelines for Monitoring and Discontinuation**

### **Monitoring Criteria**

The following laboratory abnormalities require prompt retesting:

- Neutrophil counts  $<1000$  neutrophils/mm^3; confirmed promptly by repeat testing, ideally within 3-5 days;
- Lymphocyte count  $<500$ /mm^3; confirmed promptly by repeat testing, within 48 hours;
- Platelet counts  $<75,000$  platelets/mm^3; confirmed promptly by repeat testing, ideally within 3-5 days;
- Any single hemoglobin value  $<9.0$  g/dL or one that drops  $\geq 2$  g/dL below baseline; confirmed promptly by repeat testing, ideally within 3-5 days;
- Any single AST and/or ALT elevation  $>3$  times the upper limit of normal regardless of accompanying symptoms or the total Bilirubin should prompt repeat testing. This should also prompt review of [Section 8.4.2](#); additional investigations must be conducted.

### **Temporary Interruption to Dosing**

An investigator can temporarily interrupt dosing for up to a maximum of 28 consecutive days for a subject, for safety reasons or while monitoring abnormal laboratory tests if the investigator judges that this is necessary. The investigator should use their judgement with regard to unscheduled visits/laboratory/clinical assessments required to monitor the subject during this time-frame. If within this timeframe the investigator judges that it is safe to restart dosing, then the subject may restart investigational product. If the investigator judges that it is not safe to restart dosing within this timeframe then the subject must be permanently discontinued from treatment, have an End of Treatment visit and enter the 4-week follow-up period. Doses not taken for the reasons mentioned above do not constitute protocol deviations or medication errors and should not be considered dosing errors, but should be noted in the dosing log with the reason for reduced drug consumption clearly described.

### **Discontinuation Criteria**

Subjects must be permanently discontinued from treatment if they meet any of the following criteria at any point in the study:

- Marked prolongation of the Fridericia-corrected QT (QTcF) interval to  $>500$  ms or  $>60$  ms change from screening ECG.
- Serious infection (see definition for Serious Adverse Events in [Section 8.2.3](#)).

- Any bleeding event thought to be associated with a platelet count reduction per the judgement of the investigator (or, if necessary/desired, following discussion with sponsor).
- Other adverse event, per judgment of the investigator, requiring discontinuation from treatment (or, if necessary/desired, following discussion with sponsor).
- Any adverse event or laboratory abnormality, that per the investigator's judgement requires temporary interruption to dosing of investigational product for >28 days.

NOTE: any initial lab value below must be retested, within 48 hours.

- Two sequential platelet counts  $<50,000/\text{mm}^3$ . If the subject has a platelet count  $<25,000/\text{mm}^3$ , investigational product should be temporarily withheld pending the confirmatory retest.
- Two sequential neutrophil counts  $<500/\text{mm}^3$ .
- Two sequential lymphocyte counts  $<500/\text{mm}^3$ .
- Two sequential hemoglobin assessments  $<8.0 \text{ g/dL}$  or  $\leq 30\%$  from baseline value.

Any of the following:

- Two sequential AST or ALT elevations  $>3$  times the upper limit of normal with at least one total bilirubin value  $>2$  times the upper limit of normal.
- Two sequential AST or ALT elevations  $>3$  times the upper limit of normal with an abnormal INR.
- Two sequential AST or ALT elevations  $>3$  times the upper limit of normal accompanied by symptoms consistent with hepatic injury.
- Two sequential AST or ALT elevations  $>5$  times the upper limit of normal, regardless of total bilirubin or accompanying symptoms.

**Note: Any of the above findings should prompt review of “The Potential Cases of Drug-Induced Liver Injury”, [Section 8.4.1](#) for which additional investigations must be conducted.**

- Two sequential increases in serum creatinine that are  $>50\%$  over the average of screening and baseline values AND an absolute increase in serum creatinine  $\geq 0.5 \text{ mg/dL}$ . At the time of study completion or discontinuation, if a patient should exhibit elevations in serum creatinine  $\geq 33\%$  above the average of screening and baseline values, they will be re-tested every 1 to 2 weeks until the serum creatinine elevation is fully reversed to within 10% of the average of screening and baseline values or has stabilized.

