- A positive QuantiFERON®-TB Gold (QFT-G) In-Tube test or positive Mantoux/Purified Protein Derivative (PPD) tuberculin skin test performed at or within the 12 weeks prior to Day 1.
  - It is recommended that subjects with a history of Bacille Calmette Guérin (BCG) vaccination be tested with the QFT-G test since the Mantoux/PPD tuberculin skin test may be positive due to vaccination. See [Section 7.3.4](#) for requirements for Mantoux/PPD tuberculin skin testing.
  - A negative QFT-G or Mantoux/PPD tuberculin skin test is required unless the subject has previously received a documented adequate course of therapy for either latent (9 months of isoniazid in a locale where rates of primary multi-drug TB resistance are <5% or an acceptable alternative regimen) or active (acceptable multi-drug regimen) TB infection. If the current incidence rates of multi-drug resistant TB infection in the locale are unavailable, an adequate treatment regimen should be defined as the regimen recommended by the health ministry or expert panel in the locale;
  - Chest radiograph (or chest Computed Tomography (CT) scan, if available) taken at screening with changes suggestive of active tuberculosis (TB) infection as determined by a qualified radiologist. A chest X-ray is required for adults and recommended for adolescents per local standard/guidelines, unless previously performed and documented within 12 weeks prior to Study Day 1.
  - A history of either untreated or inadequately treated latent or active TB infection;
  - A subject who is currently being treated for active TB infection is to be excluded.
19. **ANY** of the following abnormalities in clinical laboratory tests at screening, as assessed by the study-specific laboratory and confirmed by a single repeat, if deemed necessary:
- Absolute neutrophil count of  $<1.2 \times 10^9/L$  ( $<1200/mm^3$ );
  - Hemoglobin  $<10.0$  g/dL or hematocrit  $<30\%$ ;
  - Platelet count of  $<150 \times 10^9/L$  ( $<150,000/mm^3$ );
  - Absolute lymphocyte count of  $<0.50 \times 10^9/L$  ( $<500/mm^3$ );
  - Estimated Creatinine Clearance  $<40$  mL/min based on the age appropriate calculation, or serum creatinine  $>1.5$  times the upper limit of normal (ULN);
  - Aspartate aminotransferase (AST) or alanine aminotransferase (ALT) values  $>2$  times the ULN;

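### The percentage limb of the hemoglobin discontinuation rule in Protocol Appendix 4 gives no direction or reference, and neither reading of its printed wording works as a stopping threshold

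*Protocol*

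**What the plan says.** Appendix 4 of the Protocol has two tiers for hemoglobin.

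- **Monitoring Criteria.** "Any single hemoglobin value" below 9.0 g/dL, or one that has dropped by 2 g/dL or more below baseline, calls for a prompt repeat test.
- **Discontinuation Criteria.** The list opens with "Subjects must be permanently discontinued from treatment if they meet any of the following criteria". Its hemoglobin line is triggered by "Two sequential hemoglobin assessments" that satisfy either of two limbs: an absolute one, below 8.0 g/dL, and a relative one, printed as "\leq 30\%$ from baseline value" (the leading code is a less-than-or-equal sign).

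The relative limb has no word such as fall, decrease, below or of. No other part of the Protocol or SAP defines it. Comparable limits in the same appendix do carry a direction: the hemoglobin retest trigger is a drop below baseline, and the creatinine limits are increases over, or elevations above, the average of the screening and baseline values.

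**The concern.** The rule removes a subject from treatment for good, so a site has to be able to apply it from the page. The less-than-or-equal sign is natural for a low hemoglobin value but runs the wrong way for the size of a fall, and the word from suggests a change. A reader who takes the words literally gets a rule that stops subjects for small falls and keeps them on treatment after large ones. A reader who takes the percentage as a fraction of baseline gets a limb that never acts.

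The main stake is safety. Protocol Section 1.5 lists hematopoietic effects among the potential risks, hematology is scheduled at every on-site visit, and the rule applies throughout a study planned for approximately 218 sites. A secondary stake is analytical. SAP Section 5.3.3 censors subjects who permanently discontinue without a flare at their last dosing date, so differing stopping decisions would feed into censoring and into the discontinuation summaries.

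**Working it through.** The plan has no derived figure to reproduce here; this is a threshold, and the check is whether it behaves as one.

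**Inputs.** From Appendix 4: absolute limb below 8.0 g/dL; relative limb 30%; retest trigger below 9.0 g/dL or a drop of at least 2 g/dL. From Section 4.2, exclusion criterion 19: hemoglobin below 10.0 g/dL at screening is excluded. Assumption, not in the documents: baselines of 10 to 17 g/dL, with 14.0 g/dL as the worked case.

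**Readings.** With baseline b and observed value v:

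- A, change of 30% or less: (b − v)/b ≤ 0.30.
- B, fraction of baseline: v ≤ 0.30 × b. At 14.0, this is 4.2 g/dL.
- C, inferred, a level 30% under baseline: v ≤ 0.70 × b. At 14.0, this is 9.8 g/dL.

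**Outcome at b = 14.0 g/dL when the value is seen twice.** None of these values meets the absolute limb. The retest trigger is met at 12.0 g/dL or lower.

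| Value (g/dL) | Fall | Retest trigger met? | A | B | C |
|---|---|---|---|---|---|
| 13.5 | 0.5/14.0 = 3.6% | no | stop | continue | continue |
| 12.0 | 2.0/14.0 = 14.3% | yes | stop | continue | continue |
| 9.5 | 4.5/14.0 = 32.1% | yes | continue | continue | stop |
| 8.5 | 5.5/14.0 = 39.3% | yes | continue | continue | stop |

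**Across baselines of 10 to 17 g/dL.**

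- Reading A: a fall of only 0.1 g/dL is 0.6% to 1.0% of baseline and meets the limb, so discontinuation is reached before the retest trigger. Values from 8.0 g/dL up to 0.70 × b meet neither limb. That gap exists for every baseline above 8.0/0.70 = 11.43 g/dL.
- Reading B: the limit is 3.0 to 5.1 g/dL, always inside the absolute limb. It would add something only above a baseline of 8.0/0.30 = 26.7 g/dL.
- Reading C: the limit is 7.0 to 11.9 g/dL, a drop of 3.0 to 5.1 g/dL. That always exceeds the 2 g/dL retest trigger, so retesting comes first. The limb acts before 8.0 g/dL when baseline is above 11.43 g/dL.

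The three readings therefore give different stopping decisions for the same subject. A, the change reading, runs backwards. B is redundant. C works as a second tier but needs words that are not on the page.

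**The case against.** The strongest reply is that Reading C is what an experienced investigator would take from the line. The other hematology items in the list are low-value limits, so the sign may well apply to the hemoglobin value and not to the size of the change. On that reading the conflict with the monitoring tier disappears and the limb does some work. This stands in part: a reader might infer that the rule contradicts the retest trigger however it is read, and the documents do not support that. It does not make the text adequate, because the words do not state Reading C and the neighboring limits show that a direction could easily have been given.

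Three further points limit the concern.

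- A reader might infer that subjects would be withdrawn in numbers for trivial falls. That is unlikely. A site would see that the literal result is absurd, and Section 4.5 gives a route to the sponsor's medical personnel. The list also carries its own confirmation step, "NOTE: any initial lab value below must be retested, within 48 hours", and the appendix allows interruption or discontinuation on the investigator's judgment, so a subject with falling hemoglobin is not left unprotected.
- A reader might infer bias in the time-to-flare result. Nothing in the documents shows how many subjects would come near this limit. SAP Section 5.3.3 and Appendix 6 already provide tipping-point analyses for censoring at discontinuation.
- The sign may have been altered when the text was read from PDF. Neighboring signs in the appendix read coherently, which makes this less likely, but it cannot be excluded. The missing direction word remains a defect whichever sign was printed.

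The different retest times in the two tiers (ideally 3 to 5 days, and 48 hours) serve different purposes and are not part of this point.

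**Conclusion.** Wrong as written (decision threshold), minor severity. As a change of 30% or less, the limb is met by a 3.6% fall and missed by a 39.3% fall at an assumed baseline of 14.0 g/dL. As a fraction of baseline, it adds nothing to the 8.0 g/dL limb at any plausible baseline. A coherent reading exists but must be inferred, so the realistic consequence is that sites apply a mandatory safety stopping rule differently. Any effect on censoring of time to flare cannot be sized from the documents and is probably small. Sample size, power and Type I error are not affected.

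The conclusion rests on the sign being as printed and on assumed baselines of 10 to 17 g/dL. It takes no position on which threshold is clinically right or was intended.

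**What to change.** The sponsor should check the sign in the source document, then reconcile the hemoglobin lines under Monitoring Criteria and Discontinuation Criteria in Appendix 4. The discontinuation line should state whether the percentage is a fall from baseline or a fraction of baseline, and in which direction it applies. The value is for the sponsor's clinicians to set. The cost is a one-line protocol clarification communicated to sites, with no change to the design, the sample size or the SAP's methods.
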